However, it is probable that the cause of symptoms throughout the whole population of persons diagnosed with ME/CFS is not homogeneous. It is possible that all three of the aforementioned possibilities are correct, but only for subpopulations of ME/CFS sufferers. These possibilities may not be relevant to persons who credit the onset of ME/CFS with non-infectious exposures and life stressors nor those with substantial premorbid psychiatric illness. A host of unusual or poorly described medical phenomena, such as mast cell activation disorder, Chiari malformation, myotonic muscular dystrophy, paraneoplastic phenomenon that can accompany occult neoplasms, and alterations in the microbiome, may also contribute to the development of ME/CFS symptoms in certain individuals. For the purpose of reducing heterogeneity in the current study, we will only enroll patients who have a clinical history of infection followed by chronic fatigue and post-exertional malaise. We have introduced the term, post-infectious ME/CFS (PI-ME/CFS) to refer to these patients.

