# 3.3.3 Additional exclusion criteria for participants with PI-ME/CFS for exercise stress visit

1. Current (within 1 week) use of prescription or over-the-counter medications, herbal supplements, or nutraceuticals that may influence brain excitability that the potential participant is either unwilling or clinically unable to safely wean off for the duration of the period of the exercise stress visit. The possibility for a potential participant to be weaned off medication will be cooperatively determined by both the clinical investigative team and personal physicians. Examples of medications that influence brain excitability include tricyclic antidepressants, hypnotic, antiepileptic, antipsychotic medication, stimulants, antihistamines, muscle relaxants, dopaminergic medications, and sleep medications.

3.3.4 Additional exclusion criteria for healthy volunteer group

- 1. Substantial daily fatigue as determined using PROMIS-SF Fatigue: score of > 17.
- 2. Significant neurological disorder (e.g. neurodegenerative disorder, stroke, epilepsy).
- 3. Current (within 1 week) use of prescription or over-the-counter medications, herbal supplements, or nutraceuticals that may influence brain excitability

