## **12** Statistical Analysis

# 12.1 Analysis of data/ study outcomes

The studies performed under this protocol are exploratory. Quantitative research data will be acquired and logged into a database. The PI or designated investigator will monitor data integrity. Because a variety of types of data will be obtained in the study, the statistical methods most appropriate for the nature of the data will be used. Some of the relevant statistical approaches are as follows:

We are primarily interested in evaluating whether various types of data obtained are significantly different between the three groups as measured in cross-section during the phenotyping visit as well as between HV and PI-ME/CFS groups before and after an exercise stress. Each of these groups will be characterized using standard descriptive statistical methods.

As noted in Section 4.5, ME/CFS participants that are found no to meet the strict inclusion/exclusion of this study all have been diagnosed with ME/CFS by health providers and represent ME/CFS in the community. HVs and COVID-19 HVs that do not have fatigue or PEM may also be found to medical issues or other findings that would exclude them from meeting the strict inclusion/exclusion criteria of being healthy, but still represent a non-fatigue comparator to ME/CFS patients. The primary focus of the analyses detailed below will be between adjudicated ME/CFS participants and HVs and COVID-19 HVs that meet all inclusion/exclusion criteria. If the result of a primary analysis is positive, a secondary analysis will be repeated using all of participants. Findings that remain robust even when less stringent inclusion/exclusion criteria are used suggest that they are more likely to be replicable in community cohorts and perhaps worthy of further exploration.

For each continuous-scale outcome, repeated measures analysis of variance (ANOVA) will be used to test whether there are significant differences in cross-sectional measurements as well as in the pre and post measurements among two groups by using F tests. These initial tests will be performed using the adjudicated PI-ME/CFS group (i.e. participants determined to have PI-ME/CFS by the protocol's adjudication process) compared to HV and COVID-19 HV participants meeting all inclusion and exclusion criteria. The cross-sectional analyses may then be repeated using all HV and COVID-19 HV participants that did not report substantial clinical fatigue as noted above.

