If the overall multivariate test is significant, we will follow up with several post-hoc tests. Specifically, we will first conduct multivariate tests to compare the adjudicated PI-ME/CFS group (i.e. participants determined to have PI-ME/CFS by the protocol's adjudication process) vs the other two control groups, and the PI-ME/CFS group vs each of the two control groups. These analyses will initially performed using only HV and COVID-19 HV participants meeting all inclusion and exclusion criteria. As noted above, for analyses that are statistically significant, the analysis will be repeated using all HV and COVID-19 HV participants that did not report substantial clinical fatigue to determine if the results remain statistically significant when less stringent inclusion/exclusion criteria are applied.

Second, univariate ANOVA will be used for both cross-sectional measurements and pre and post exercise measurements separately to identify differences among groups. A
similar univariate analysis will be conducted for the measurements of change from pre- to post exercise using the univariate ANOVA.

Additionally, descriptive statistics will be used to characterize the entire group of ME/CFS participants that completed the phenotyping evaluation regardless of adjudication. Comparisons will be made between the adjudicated PI-ME/CFS group and the phenotyping ME/CFS group. If there is no significant difference between the above two groups, it is not necessary to compare a ME/CFS group to our two control groups. Where statistically appropriate, the ANOVA methods described above will be used to compare the ME/CFS group with the two control groups.

Statistical approaches such as chi-square tests and multinomial logistic regression models will be used to examine the group differences for categorical outcomes.

A level of significance is set at 0.05. Multiple comparison test procedures such as Bonferroni and Dunnett's methods will be used to examine the differences in each outcome measure among groups.

The primary MRI imaging aim is to test whether PI-ME/CFS group has significantly different connectivity patterns compared to the HV control group.

To this end, functional MRI measures will be taken at three conditions: 1) performing a force task, 2) performing a cognitive task, to define a network of interest, and 3) at rest to compute functional connectivity. At each condition, fMRI will be measured at two time points: pre exercise (preEx) and post exercise (postEx).

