# 12.2 Power analysis

The accrual ceiling for participants in the phenotyping and exercise stress arms of this study is 150 participants (50 per group) and dropouts will be replaced. The sample sizes were chosen based on convenience and equals about 1-2 participants per week. This is a phase I pilot study intended to explore a variety of clinical and biological data from the three different groups. For neuroimaging studies of somatosensory stimulation, it is estimated to require 12 subjects to achieve 80% power at the threshold of 0.05 to determine differences at the single voxel level for typical activations. The proposed sample size of 20 participants per group should be adequate for distinguishing group differences in fMRI activity during the proposed fatiguing tasks. The study is exploratory and its results will be used to estimate effect sizes to design a larger clinical study.

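### Section 12.1 names only ANOVA-type tests, normally run with one pooled variance, for continuous outcomes; if PI-ME/CFS is the more variable group, the three-group Visit 1 contrasts can exceed 5%, and separate-variance tests would prevent this cheaply.

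*Combined protocol and SAP*

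**What the plan says.** Section 12.1 states that "repeated measures analysis of variance (ANOVA) will be used to test whether there are significant differences in cross-sectional measurements" and in pre/post measurements, by F tests, for each continuous-scale outcome. If the overall multivariate test is significant, it plans contrasts of the adjudicated PI-ME/CFS group "vs the other two control groups, and the PI-ME/CFS group vs each of the two control groups", and then univariate ANOVA. It adds "A level of significance is set at 0.05" and "Multiple comparison test procedures such as Bonferroni and Dunnett's methods will be used". It names no separate-variance test and no check of equal variance for continuous outcomes. It does allow latitude: "the statistical methods most appropriate for the nature of the data will be used", with the listed methods given as some of the relevant approaches.

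On group sizes, section 3.1 targets 20 completers per group, and section 12.2 sets the ceiling at "150 participants (50 per group) and dropouts will be replaced". Section 12.1 also plans to repeat significant analyses with all HV and COVID-19 HV participants who lack substantial fatigue, and not only those meeting every criterion.

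On spread, section 1.3 expects that the cause of symptoms "throughout the whole population of persons diagnosed with ME/CFS is not homogeneous" and that different mechanisms may hold in different subpopulations. Sections 3.3.4 and 3.3.5 exclude controls with "Substantial daily fatigue as determined using PROMIS-SF Fatigue: score of > 17". Section 3.2.3 restricts patients too, through MFI and SF-36 cut-offs and unanimous adjudication.

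**The concern.** A pooled error variance averages the groups' variances. With two narrow control groups and one wide patient group, the average falls below what a patient-versus-control contrast needs. Its standard error is then too small and the test rejects too often.

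These contrasts bear directly on the primary objective. Significance also decides which analyses are repeated in the wider control sample, and it helps to select markers for ROC analysis. Equal group sizes remove most of this problem when only two groups are compared. They do not remove it when three groups share one error term.

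**Working it through.** **Inputs.** From the documents: alpha 0.05 (section 12.1), taken as two-sided; three groups at Visit 1 and two at Visit 2 (section 4.1); target 20 per group (section 3.1). Assumed, because the documents give no SDs: the ratio r of patient SD to control SD, over the range 0.5 to 3; normal data; unequal sizes where stated. Rejection rates are simulated with no true difference in the contrast tested.

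**The plan's own figure.** With r = 1 at 20/20/20 the pooled contrasts, the overall F test and Dunnett all reject 5.0%. The nominal level is reproduced when variances are equal.

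**Standard error at equal n, three groups, control SD = 1.**
- Expected pooled variance: (r² + 2)/3.
- Versus one control: pooled variance 2(r² + 2)/(3n), true variance (r² + 1)/n, ratio 2(r² + 2)/[3(r² + 1)]. At r = 2 this is 12/15 = 0.80, so the standard error is √0.80 = 0.894 of its true value.
- Versus the mean of both controls: pooled variance (r² + 2)/(2n), true variance (r² + 0.5)/n, ratio (r² + 2)/(2r² + 1). At r = 2 this is 6/9 = 0.667, so the standard error is 0.816 of its true value.
- Approximate rejection rate: 2[1 − Φ(1.96 × √ratio)], which gives 8.0% and 11.0% at r = 2.

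**Simulated rates at 20/20/20, before any gate; the two contrast rows are also unadjusted for multiplicity.**

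| | r = 1.5 | r = 2 | r = 3 |
|---|---|---|---|
| Versus one control | 6.8% | 8.0% | 9.8% |
| Versus both controls | 8.4% | 11.0% | 13.9% |
| Dunnett, family-wise | 6.7% | 7.7% | 8.6% |
| Overall F | 5.5% | 6.2% | 7.4% |

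**With an overall gate.** The plan gates on a multivariate test. A univariate F test stands in for it here, with unadjusted contrasts behind it and r = 2.
- 20/20/20, no differences anywhere: 4.8% versus HV and 5.8% versus both.
- 20/20/20, PI-ME/CFS equal to HV but COVID-19 HV shifted: the PI-ME/CFS versus HV contrast rejects 7.6% when the shift is one control SD, and about 8.1% once the shift is large enough to open the gate almost always.
- 20/30/30, no differences anywhere: 7.9% versus HV and 9.0% versus both.

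**Other cases.**
- Fewer patients than controls, r = 2: Dunnett without a gate gives 12.0% at 20/30/30.
- Patients less variable (r = 0.5, 20/20/20): 3.3% versus one control, Dunnett 3.3%.
- Patients more variable and more numerous (r = 2, 50/20/20): Dunnett 1.5%.
- Visit 2, two groups of 20: the pooled and Welch standard errors are identical, and the pooled test rejects 5.1%, 5.2% and 5.4% at r = 1.5, 2 and 3. At 20 patients and 30 HV with r = 2 it rejects 8.5%.

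**Separate variances.** Two-group Welch tests reject 4.9% to 5.1% in every setting tried. For PI-ME/CFS versus each control, Welch with Bonferroni has a family-wise error of 3.2% to 5.0%; at 20/20/20 and r = 2 it is 4.0%, against 7.7% for Dunnett.

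**The case against.** A reader might infer that the groups differ in spread and size by design, so that the 0.05 level is certainly exceeded. The documents do not support that. Target and ceiling are equal across groups, dropouts are replaced, and no SD is given. The heterogeneity remark in section 1.3 concerns everyone diagnosed with ME/CFS. The same paragraph says that enrolment is limited to post-infectious cases in order to reduce heterogeneity, and section 3.2.3 narrows the group further. This stands, and the spread ratio remains an assumption. Some heterogeneity may nevertheless persist after enrolment, because the three mechanisms described in section 1.3 can each follow an infection.

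The ungated rates also overstate what the plan would do with equal groups and no differences, since section 12.1 tests contrasts only after a significant overall test. That stands for the complete null at 20/20/20. It does not stand when the two controls differ, or when controls outnumber cases. The planned repeat with all non-fatigued controls can create the second situation, because it can enlarge the control groups while the cases stay the adjudicated ones. A 20/50/50 split would give much larger errors, but it is an extreme that the plan does not call for, and the reverse imbalance is mostly conservative.

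Finally, the study is exploratory and the plan permits the most appropriate method, so ANOVA is not locked in. That lowers the weight of the point. It does not settle which test is used, because the only method then named for every continuous outcome is ANOVA and no rule says when to leave it. Nor does the plan say outright that pairwise contrasts take their error from all three groups; that is the standard form. Run as separate two-group tests at 20/20, they would be near nominal.

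**Conclusion.** The point holds conditionally. Section 12.1 names methods that in standard form pool the variance, and gives no separate-variance version. If PI-ME/CFS is the more variable group, three-group Visit 1 contrasts with a pooled error have standard errors that are too small even at the planned sizes. For an SD ratio of 1.5 to 3, the one-control standard error is 7% to 14% too small (0.934 to 0.856 of its true value).

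The excess is small behind the overall gate at equal sizes under a complete null. It becomes material when the control groups differ or when cases are the smaller group. The tempting broader reading, that every comparison is anti-conservative, fails: Visit 2 at equal sizes is at most about 5.4%, and some configurations are conservative. All figures rest on assumed SD ratios and normal data. The multivariate tests and the fMRI regression were not simulated. Label: cheap improvement.

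**What to change.** In section 12.1, for continuous outcomes compared across the three groups at Visit 1, name Welch's ANOVA. Test the PI-ME/CFS contrasts with separate group variances and Satterthwaite degrees of freedom, using Bonferroni or Games-Howell in place of pooled-variance Dunnett. Apply the same tests when the analysis is repeated with all non-fatigued controls. At Visit 2, use separate group variances when the PI-ME/CFS and HV sizes differ.

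The cost is a sentence or two in section 12.1 and a software option. If variances are in fact equal, power for a difference of 0.8 SD at 20 per group falls from about 70% to 69%. The change does not address the multivariate gate, which would need its own statement if it is kept.

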All PI-ME/CFS phenotyping participants will have a ME/CFS diagnosis from their health care providers and, therefore, represent the illness as it is considered in the community. For this reason, PI-ME/CFS participants will undergo all of the phenotyping procedures even if information that would exclude the participant from the study is discovered during the visit. Data collected from PI-ME/CFS participants that fail to meet *exercise stress* criterion will be used in comparative analyses and serve as a control group for comparisons to PI-ME/CFS participants that qualify for the exercise stress visit.

Two other control groups have also been chosen for comparisons.

The healthy volunteer (HV) group will consist of demographically matched persons without clinical fatigue, free from medical disease, and presumed to have a properly functioning immune system. The HV group represents a standard control population for comparison to the PI-ME/CFS group. HV participants will take part in both the phenotyping and exercise stress visits.

Asymptomatic persons with a history of COVID-19 infections and a full recovery is a salient comparator group to PI-ME/CFS. Similar to PI-ME/CFS, COVID-19 has been implicated in causing a syndrome of fatigue, pain, and neurocognitive difficulties, currently referred to as "long haul COVID". The COVID-19 HV group will consist of healthy persons who had a laboratory documented COVID-19 infection within the last 5 years and currently do not have clinically significant fatigue and PEM. The COVID-19 HV control group will allow for biological amongst persons with an infectious process that did not progress to chronic debility. COVID-19 HV participants will take part in the phenotyping visit but not the exercise stress visit of the protocol.

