
We will use a multivariate regression model where the response variable is connectivity strength among regions of interest pre- and post- exercise. Predictors include group status and fatigue scores.

Region of interest for the connectivity analysis will be defined based on tasks 1) and 2). For this, data will be pre-processed with standard techniques using AFNI. Imaging quality assurance will be performed (i.e. motion correction parameters). We will fit a multivariate regression model to detect the differences in activity patterns of each task. Behavior and scales of fatigue will be entered as covariates.

Significance of the results will be set at p = 0.05 corrected for multiple comparisons for all analyses.

Lastly, we will conduct receiver operating characteristic (ROC) analysis for selected markers that are potentially important, which will be identified by exploratory analysis and several statistical approaches mentioned above. We will evaluate the accuracy of each marker for its ability to classify subjects in the PI-ME/CFS group from those in the HV control group. For example, if MRI imaging measurements are significantly different among groups, next, we will calculate the nonparametric area under the ROC curve (AUC) for each imaging marker and its 95% confidence interval.

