# 13 Human Subjects Protection

# 13.1 Subject selection

Subject selection will be equitable among eligible participants. ME/CFS is reported to happen most commonly in persons aged 40-59. Increasing age also has significant effects of both on the experience of daily fatigue and on brain physiology. For this reason, individuals over the age of 60 will be excluded. Several of the neurocognitive instruments being used in this protocol require a 7th grade education for proper administration. These include the MMPI2, the Controlled Oral Word Association, and Grooved Pegboard tests. For this reason, persons with less than a 7th grade education will be excluded.

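### No planned group comparison adjusts for age or sex, which leaves the phenotyping contrasts with the unmatched COVID-19 HV group open to demographic confounding

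*Combined protocol and SAP*

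**What the plan says.** **Analysis (section 12.1).** For each continuous outcome, "repeated measures analysis of variance (ANOVA) will be used to test whether there are significant differences in cross-sectional measurements", and pre- and post-exercise measurements are tested the same way. If the overall multivariate test is significant, follow-up tests compare PI-ME/CFS with the two control groups together and with each one. Then "univariate ANOVA will be used for both cross-sectional measurements and pre and post exercise measurements separately to identify differences among groups". For the rest, "Statistical approaches such as chi-square tests and multinomial logistic regression models will be used to examine the group differences for categorical outcomes". Two fMRI regressions do list their terms. For connectivity, "Predictors include group status and fatigue scores"; for task activity, "Behavior and scales of fatigue will be entered as covariates". Age and sex appear in none of these models, and section 12.3 does not add them.

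**Groups (section 3.1).** The HV group consists of "demographically matched persons without clinical fatigue"; the matching variables and tolerances are not given. For the other control group, "The COVID-19 HV group will consist of healthy persons who had a laboratory documented COVID-19 infection within the last 5 years". No matching of that group is mentioned there, in its eligibility criteria (3.2.5, 3.3.5) or in the recruitment text (4.2).

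**Age (sections 3.2.1 and 13.1).** Ages 18 to 60 are allowed in all three groups. Section 13.1 states that "Increasing age also has significant effects of both on the experience of daily fatigue and on brain physiology", but uses this only to justify the upper age limit.

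**The concern.** In a comparison of non-randomised groups, a difference in age or sex mix shows up as a group difference in any outcome that depends on age or sex. Matching or adjustment can prevent this. The HV comparison has some of the first; the COVID-19 HV comparison has neither.

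The protocol gives some reason to expect imbalance. Section 13.1 reports ME/CFS as most common at ages 40 to 59, and section 4.32, on focus-group recruitment, names men and people aged 18 to 29 among under-represented ME/CFS subgroups. Nothing steers an unmatched COVID-19 HV group towards that profile.

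No other step in 12.1 would expose the problem. Bonferroni and Dunnett procedures deal with multiplicity, not bias. Positive findings are re-run under looser eligibility, but a demographic artefact could survive that re-run and then be read as more likely to replicate.

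The results matter beyond this study. Section 12.2 uses them to estimate effect sizes for a larger one, and section 4.1 treats negative results as a guide to where large differences are unlikely. Confounding can create a difference or hide one, so it affects both uses.

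**Working it through.** The plan has no figure for imbalance or covariate effect, so there is nothing to reproduce. The check asks how large the problem would be under stated assumptions.

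**Inputs from the documents.** Target of 20 completers per group (3.1); ceiling of 50 per group and significance level 0.05 (12.2, 12.1). The test is taken as two-sided, which the plan does not state.

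**Assumed shifts.**
- Sex: a 20-point difference in sex mix and a 1 SD sex effect give 0.20 × 1 = 0.20 SD.
- Age: a 5-year gap at 0.03 SD per year gives 5 × 0.03 = 0.15 SD.
- Both together: 0.20 + 0.15 = 0.35 SD if they act in the same direction, and 0.20 − 0.15 = 0.05 SD if they oppose.

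**False-positive rate with no true difference.** For a spurious shift of δ SD and n per group, the two-group statistic is noncentral t with 2n − 2 degrees of freedom and noncentrality δ√(n/2). The rate is the probability that its absolute value exceeds the critical value: 2.024 for n = 20 and 1.984 for n = 50.

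| δ (SD) | Noncentrality, n = 20 | Rate, n = 20 | Noncentrality, n = 50 | Rate, n = 50 |
|---|---|---|---|---|
| 0.15 | 0.474 | 7.5% | 0.750 | 11.5% |
| 0.20 | 0.632 | 9.5% | 1.000 | 16.8% |
| 0.30 | 0.949 | 15.2% | 1.500 | 31.8% |
| 0.35 | 1.107 | 19.0% | 1.750 | 41.0% |
| 0.40 | 1.265 | 23.4% | 2.000 | 50.8% |

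**Does adjustment remove it?** A simulation (20,000 runs per cell, no true group effect) shifted one group by D SD on a covariate with correlation r to the outcome, so that δ = rD.

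| D | r | δ | Unadjusted, n = 20 | Unadjusted, n = 50 |
|---|---|---|---|---|
| 0.25 | 0.3 | 0.075 | 5.6% | 6.4% |
| 0.5 | 0.5 | 0.25 | 12.3% | 23.4% |
| 0.8 | 0.5 | 0.40 | 23.3% | 51.2% |

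The unadjusted three-group F test gave similar rates (5.7%, 11.5% and 22.6% at n = 20). With the covariate in the model, the rate was 4.7% to 5.3% in every cell. A small imbalance barely matters; a moderate one at least doubles the nominal rate.

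**Which comparisons are exposed.** COVID-19 HV participants attend only the phenotyping visit (3.1, 4.1). The exposed contrasts are PI-ME/CFS versus COVID-19 HV, and PI-ME/CFS versus both control groups together. If only the COVID-19 HV group is imbalanced and the two controls weigh equally, the second contrast carries half the shift. The exercise contrasts (4.1), the primary MRI aim and the ROC analysis (12.1) set PI-ME/CFS against HV.

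**The case against.** The strongest reply is that the plan is silent on covariates and does not reject them. Section 12.1 introduces its methods as some of the relevant approaches, promises whatever suits the data, and section 12.3 leaves each analysis to people experienced with that data type. This stands in part. A reader might infer that the plan prescribes a model with group as its only factor, or that every comparison is an unadjusted ANOVA. The text supports neither: it nowhere excludes covariates, categorical outcomes and fMRI use other models, and the fMRI models do carry covariates. But a general promise of suitable methods commits nobody to adjustment, and where 12.1 does list covariates, age and sex are absent.

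The second reply concerns scope. The exercise, MRI and ROC comparisons use a group described as matched, and change scores remove stable differences in level between people. Both points stand. The protection is incomplete, however: the matching variables are undefined, and the primary analysis set is cut after enrolment by adjudication and full eligibility, so the analysed groups may no longer match. Change scores also do not remove differences in response to exercise.

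Third, recruitment routes overlap. Section 4.2 allows all three groups to come through the same recruitment office or by self-referral. That weakens any presumption of a large imbalance but does not exclude one.

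Fourth, the magnitudes are assumed. That stands. Either assumed bias alone gives only 7.5% or 9.5% at 20 per group, and the two could offset. Section 12.1 also plans multiple-comparison procedures: at an illustrative 0.025 for two control contrasts, shifts of 0.3 and 0.4 SD give 9.4% and 15.5% at 20 per group, against a nominal 2.5%. The figures for 50 per group describe the accrual ceiling, not the completion target.

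Finally, BMI may be partly a consequence of illness or inactivity, so adjusting for it could remove part of a real phenotype. That stands, and keeps BMI out of the main model.

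**Conclusion.** The point holds as an omission that creates a risk. No comparison in 12.1 adjusts for age or sex, although the protocol itself says age affects fatigue and brain physiology. The exposure is greatest for the phenotyping contrasts that involve the COVID-19 HV group, which has neither described matching nor adjustment; it is smaller for the comparisons against HV.

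Under assumed shifts of 0.15 to 0.4 SD, the two-group false-positive rate at an uncorrected 0.05 is about 7.5% to 23% at 20 per group and 11.5% to 51% at 50 per group. These figures rest wholly on the assumed imbalance and covariate effects; a shift below 0.1 SD would do little harm. A reader might infer that the study's group differences will be demographic artefacts. The documents do not support that, because they report no imbalance. They support only that the plan, followed as written, could not separate such an artefact from a disease effect. The exploratory purpose lowers the stakes but does not remove them, since the estimates feed the next study.

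**What to change.** In section 12.1:
- Fit each continuous outcome as a linear model (a mixed model for repeated measurements) with group, age and sex.
- Add age and sex to the logistic models for categorical outcomes and to both fMRI regressions.
- Report the unadjusted results alongside as supportive.
- Use BMI only in a sensitivity model for metabolic, exercise, microbiome and blood-marker outcomes, and say why.

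In section 3.1, state the variables on which HV participants are matched.

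The cost is about two degrees of freedom (with three groups of 20, residual degrees of freedom fall from 57 to 55) and a little more analysis work. Age is already needed for eligibility, and sex should be on record from the clinical assessment. The BMI model needs height and weight in the COVID-19 HV group; section 4.5.1 mentions vital signs without naming these, so that should be confirmed. Section 12.3 describes the interim analysis as covering only the ME/CFS and HV cohorts, so the rule for COVID-19 HV comparisons can still be set before those comparisons are analysed.

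### Section 12.1, as worded, compares the adjudicated PI-ME/CFS group with a phenotyping group that contains it, unlike section 3.1; an independent-groups test on those sets would be strongly conservative

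*Combined protocol and SAP*

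**What the plan says.** Section 12.1 defines the adjudicated group as "participants determined to have PI-ME/CFS by the protocol's adjudication process". Near the end of its account of the ANOVA methods it says that "descriptive statistics will be used to characterize the entire group of ME/CFS participants that completed the phenotyping evaluation regardless of adjudication". The next sentence is the one at issue: "Comparisons will be made between the adjudicated PI-ME/CFS group and the phenotyping ME/CFS group". The label for the second group is not defined separately, and its nearest antecedent is the entire phenotyped group.

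The result then has a use: "If there is no significant difference between the above two groups, it is not necessary to compare a ME/CFS group" to the two control groups. After that comes "Where statistically appropriate, the ANOVA methods described above will be used to compare the ME/CFS group with the two control groups". The significance level is given once for the section: "A level of significance is set at 0.05".

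Section 3.1 describes the comparison differently. There, the PI-ME/CFS participants who do not meet the exercise stress criteria "serve as a control group for comparisons to PI-ME/CFS participants that qualify for the exercise stress visit". Under that description nobody is in both groups.

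**The concern.** Every adjudicated case has completed phenotyping, because adjudication follows that visit (section 4.5.25). A phenotyping group taken regardless of adjudication therefore contains all of the adjudicated group. The group-comparison methods that 12.1 names (ANOVA F tests, chi-square tests, multinomial logistic regression) take each participant to be in one group only, and nothing in 12.1 allows for overlap.

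Testing a part against its whole does two things. It dilutes the contrast, because the adjudicated participants sit on both sides. It also ignores the positive covariance between the two means, so the standard error is too large. Both push towards non-significance.

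That direction matters because non-significance is the outcome that releases the plan from comparing the wider ME/CFS group with the controls. Section 4.1 also treats negative results as informative about where large differences are unlikely, so a built-in tendency towards them is not harmless in an exploratory study.

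**Working it through.** The documents give no sample size, effect size or power for this comparison, so there is no stated figure to reproduce.

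**Inputs.** Level 0.05 (12.1). Ceiling of 50 PI-ME/CFS participants (3.1, 12.2). Target of 20 participants per group completing all procedures (3.1). The adjudicated share is not stated. I assume 20 adjudicated as the main case and vary both numbers. Outcomes are taken as normal with SD 1 in each subgroup.

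**Notation.** A = adjudicated, n_A; B = phenotyped but not adjudicated, n_B; T = all phenotyped, n_T = n_A + n_B.

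**Step 1, the contrast.** mean_A − mean_T = (n_B/n_T)(mean_A − mean_B). The true difference is multiplied by the non-adjudicated fraction: 30/50 = 0.60 at 20 of 50, and 10/30 = 0.33 at 20 of 30.

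**Step 2, the standard error.**
- True variance: s²(n_B/n_T)²(1/n_A + 1/n_B) = s²(1/n_A − 1/n_T).
- Variance used by an independent-groups test: s²(1/n_A + 1/n_T).
- Ratio of standard errors: √[(n_T + n_A)/(n_T − n_A)].

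At 20 of 50: √(0.05 + 0.02) = 0.265 against √(0.05 − 0.02) = 0.173, ratio 1.53. At 20 of 30: √(0.05 + 0.0333) = 0.289 against √(0.05 − 0.0333) = 0.129, ratio 2.24.

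**Step 3, the size.** Approximately 2[1 − Φ(1.96 × ratio)]. At 20 of 50, 1.96 × 1.528 = 2.99, giving 0.0028 (0.0022 by simulation). At 20 of 30, 1.96 × 2.236 = 4.38, giving about 0.00001.

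**Step 4, rejection when the subgroups truly differ.** The overlapping test was simulated with 50,000 replicates per cell. Power for the separate-groups test comes from the noncentral t distribution.

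| Adjudicated of phenotyped | SE ratio | Size (nominal 0.05) | Overlapping: rejection at 0.5 / 0.8 / 1.0 / 1.2 SD | Separate groups: power at the same differences |
|---|---|---|---|---|
| 10 of 50 | 1.22 | 0.016 | 14 / 39 / 61 / 79% | 28 / 60 / 79 / 91% |
| 20 of 50 | 1.53 | 0.0028 | 8 / 33 / 59 / 81% | 40 / 78 / 92 / 98% |
| 25 of 50 | 1.73 | 0.0007 | 4 / 20 / 43 / 68% | 41 / 79 / 93 / 99% |
| 20 of 40 | 1.73 | 0.0007 | 2 / 12 / 27 / 49% | 34 / 69 / 87 / 96% |
| 20 of 30 | 2.24 | 0.00001 | 0.02 / 0.15 / 0.6 / 1.7% | 24 / 51 / 70 / 85% |
| 20 of 25 | 3.00 | below 0.000001 | about 0% throughout | 16 / 33 / 48 / 63% |

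The size column is the large-sample value. The loss grows with the adjudicated share.

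**Step 5, what the overlap buys.** Nothing. With the correct variance, the part-whole contrast is the separate-groups contrast times a constant, so it carries the same information.

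**The case against.** The strongest reply is that the plan does not commit to this analysis. The sentence about everyone regardless of adjudication concerns descriptive statistics, the comparator in the next sentence is undefined, and 3.1 gives the separate-groups comparison in plain terms. No test is attached to the comparison. ANOVA is named for a different contrast, ME/CFS against the controls, and only where appropriate; 12.1 also opens by promising methods suited to the data. A careful analyst could do the right thing.

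This stands in part. A reader might infer that an independent-groups ANOVA on overlapping sets is what the plan prescribes; the documents do not support that as fact. They support a conflict between 3.1 and 12.1, with 12.1 pointing to the overlapping version and offering no method that handles it. The reference to a significant difference shows that some test is intended.

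It can also be said that the effect is limited. The primary comparison, adjudicated cases against controls, is untouched. The error adds no false positives to this comparison. Section 12.1 also mentions repeating positive primary analyses with all participants, although its later, more specific text applies this to the control groups only. All of this is fair, and it keeps the point to a secondary analysis. It does not remove the use of non-significance as a reason to omit a further comparison.

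**Conclusion.** The point holds as a conflict between sections with a real statistical consequence if the text of 12.1 is followed. An independent-groups test on the overlapping sets would be conservative at every split examined. At 20 of 50, the one built from the documents' own figures, power at 0.8 SD falls from 78% to 33%. At 20 of 30 the test is close to inert.

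A reader might infer that the comparison has almost no chance of rejecting. That is true only under no difference, for small differences, or when most phenotyped participants are adjudicated as cases. At 20 of 50 a 1 SD difference is still detected 59% of the time and a 1.2 SD difference 81%. The documents do not give the adjudicated share, so the loss can only be stated as a range.

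The figures rest on three assumptions: the second group includes the adjudicated cases, the test ignores the overlap, and outcomes are normal with equal SD. The direction of the bias depends only on the first two.

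**What to change.** In 12.1, replace the comparison sentence with one that names two separate groups: phenotyped ME/CFS participants adjudicated as PI-ME/CFS, and those phenotyped but not so adjudicated, in line with 3.1. Because 3.1 splits on qualifying for the exercise stress visit, which also depends on criteria such as medication use (3.3.3), the sentence should say where an adjudicated case who does not qualify is counted.

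Name the test, and report the difference with its 95% CI so that a non-significant result is not taken as evidence of similarity. Keep the entire phenotyping group for descriptive statistics and for its own comparison with the two control groups, without making that comparison depend on this test.

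The cost is a short edit to 12.1, with no new data or procedures. Section 12.3 says that interim analysis of the cohorts completed as of October 2020 has already been initiated; if this comparison has been run on overlapping groups, it should be rerun.
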